12.2 ADVERSE EVENTS REPORTING PROCEDURES

12.2.1 GENERAL

All AEs (e.g., any new event or worsening in severity or frequency of a pre-existing condition or laboratory finding) with an onset date after the subject signs the informed consent for participation in the clinical trial must be promptly documented on the AE eCRF via the electronic data capture (EDC) system. Details of the event must include severity, relationship to study drug(s), duration, action taken, and, for SAEs only, outcome. Whenever possible, reporting specific diagnoses is preferred when reporting AEs in the AE eCRF rather than reporting individual signs and symptoms.

All AEs will be collected from the time the subject signs informed consent through 30 days after receiving the last dose of study drug(s). If initiation of new anticancer therapy occurs within 30 days following the last dose of study drug(s), the date of new anticancer therapy will be recorded on the appropriate eCRF. In addition, the investigator should report any AEs that may occur after this time period which are assessed to have a reasonable possibility of being associated with study drug.

All AEs that are considered related to study drug and all SAEs regardless of relationship to study drug must be followed to resolution or stabilization if improvement is not expected. Adverse events which completely resolve and then recur should be recorded as new AEs. For subjects who complete the EOT visit less than 30 days following the last dose of study drug, a follow-up of ongoing AEs should be documented in the subject's source file. Adverse events continuing at 30 days after the last dose of study treatment should have a comment in the source file by the investigator that the event has stabilized or is not expected to improve.

The investigator is responsible for evaluating all AEs, obtaining supporting source documents, and determining that documentation of the event is adequate. The investigator may delegate these duties to subinvestigators and must ensure that these subinvestigators are qualified to perform these duties under the supervision of the investigator and that they are listed on the FDA Form 1572.

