13.3.3.1 Adverse Events

Treatment-emergent adverse events are defined as AEs that start on or after the first day study treatment is administered and within 30 days of the last administration of study treatment. The reported AE term will be coded using MedDRA and will be graded for severity using NCI-CTCAE Version 4.03. The causal relationship between the occurrence of an AE and each treatment will be assessed by the investigator as related or not related.

Treatment-emergent adverse events will be summarized based on the number and percentage of subjects experiencing events by treatment group and by MedDRA system organ class (SOC) and preferred term. In the event that a patient experiences repeated episodes of the same AE, the subject will be counted once within each SOC and similarly counted once within each preferred term and the event with the highest severity grade and/or strongest causal relationship to each treatment will be used for purposes of incidence tabulations.

Tabular summaries of the following will be provided:

- All TEAEs by SOC
- All TEAEs in decreasing order of frequency
- TEAEs by causal relationship to study drug
- TEAEs by maximum severity grade
- All SAEs by SOC
- All SAEs in decreasing order of frequency
- TEAEs resulting in modification (i.e., dose reduction or dose interruption) of study treatment
- TEAEs resulting in discontinuation of study treatment
- Deaths within 30 days of the last administration of study treatment
- All AEs, including TEAEs, will be included in individual patient listings.

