3.1 Study Design

This is an open label, multicenter, randomized Phase 3 study comparing once weekly carfilzomib dosing in combination with dexamethasone to twice weekly carfilzomib dosing in combination with dexamethasone in subjects with relapsed and refractory multiple myeloma, 2 or 3 prior therapies, and previously treated with a proteasome inhibitor and an IMiD. The primary endpoint is PFS. The study design is illustrated in Figure 1.

Eligible subjects will be randomized in a 1:1 ratio to receive a regimen consisting of either once-weekly or twice weekly carfilzomib in combination with dexamethasone.

The randomization will be stratified by:

- International Staging System (ISS) Stage at study entry (Stage 1 versus Stage 2 or 3) per International Myeloma Working Group (Greipp 2005).
- Refractory to bortezomib treatment (Yes versus No)
- Age (< 65 versus ≥ 65 years)

Study treatment will be administered in 28 day cycles. Subjects will receive the study treatment determined by randomization until disease progression, unacceptable toxicity, withdrawal of consent, or death (whichever occurs first). No crossover between the 2 treatment groups will be allowed.

Following termination of study treatment, all subjects will be followed for disease status (if progressive disease [PD] has not been reached), subsequent antimyeloma treatment, and survival.

[figure not shown]
All subjects will be followed for safety for at least 30 additional days after the last study treatment administration. All treatment-related adverse events (AEs) and serious adverse events (SAEs) will be followed until resolution or stabilization.

Statistical Analysis Plan: 20140355

Date: 09 Jun 2017 Page 9

Figure 1 Study 20140355 Schema

ECOG = Eastern Cooperative Oncology Group; IMiD = immunomodulatory agents; IV = intravenous(Iy); ORR = overall response rate; OS = overall survival; PD = disease progression; PFS = progression-free survival; PI = proteasome inhibitor; PO = orally.

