Duration of treatment with carfilzomib and dexamethasone will be defined as the time from the first start date of each drug to the last stop date of the drug. Duration of the whole study treatment will be from the earliest start date among the two drugs to the latest stop date among the two drugs.

End of Study Treatment Date

The end of study treatment date is the date the decision was made to end investigational product reported on the end of investigational product administration CRF.

End of Study

For an individual subject: a subject ends the study in the event of death, , consent withdrawal, or lost to follow-up. The end of study date will be captured on the end of study CRF.

For the study as a whole: the end of study as a whole is defined as the time when the last subject is assessed or receives intervention for the purposes of final collection of data for the final analysis of PFS, which will be triggered when 350 PFS events (PD or death) are reported or by end of year 2018, whichever is earlier. Subjects who have not

Statistical Analysis Plan: 20140355

Date: 09 Jun 2017 Page 15

completed all expected treatment at the time of the end of study as a whole will continue to follow protocol specified treatment and procedures until completion.

Enrollment Date

The date of enrollment is the date the subject gets randomized.

Fluorescent in Situ Hybridization (FISH) Risk Group

The subjects with genetic abnormalities t(4;14), t(14;16), and deletion 17p, as indicated on FISH/Conventional Cytogenetics CRF are categorized in the high risk group. The other subjects are in the standard risk group.

International Staging System (ISS) Stage at Baseline

ISS stage at baseline will be calculated using serum beta-2 microglobulin and serum albumin values collected at baseline, based on the criteria published by the International Myeloma Working Group (Greipp 2005):

[figure not shown]
Stage I: Serum beta-2 microglobulin < 3.5 mg/L and serum albumin ≥ 3.5 g/dL

Stage II:Serum beta-2 microglobulin < 3.5 mg/L and serum albumin < 3.5 g/dL or Serum beta-2 microglobulin 3.5–<5.5 mg/L irrespective of the serum albumin

Stage III: Serum beta-2 microglobulin ≥ 5.5 mg/L

Last Dose Date of Study Treatment

[figure not shown]
It is the latest date of drug taken among carfilzomib and dexamethasone.

Statistical Analysis Plan: 20140355

Date: 09 Jun 2017 Page 16

Overall Response Rate (ORR)

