Time to response will be calculated only for subjects who achieve a best overall response of PR or better, i.e., sCR, CR, VGPR, or PR. It will be calculated in months from randomization date to the earliest date a response of PR or better is first achieved and subsequently confirmed:

Time to Response=(response start date-randomization date +1)/30.4

Treatment-emergent Adverse Event

Statistical Analysis Plan: 20140355

Date: 09 Jun 2017 Page 20

AEs starting on or after first dose of investigational product as determined by the flag indicating if the adverse event started prior to the first dose on the Events CRF and up to and including 30 days after the end of study treatment.

7. Analysis Subsets

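### The SAP's treatment-emergent window ends at a phrase whose closest defined date is the decision to stop treatment, not the last dose that the protocol uses

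*SAP*

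**What the plan says.** The SAP's definition of a treatment-emergent adverse event (Section 6) closes the window "up to and including 30 days after the end of study treatment". It names no date variable. Section 6 contains three candidates for that end point:

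- *End of Study Treatment Date*: "The end of study treatment date is the date the decision was made to end investigational product". This is a CRF date.
- *Duration of Study Treatment*: the whole treatment period runs "to the latest stop date among the two drugs".
- *Last Dose Date of Study Treatment*: "It is the latest date of drug taken among carfilzomib and dexamethasone".

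The protocol's definition (13.3.3.1) places treatment-emergent events "within 30 days of the last administration of study treatment". The same section lists a table of "Deaths within 30 days of the last administration of study treatment".

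**The concern.** The SAP phrase almost repeats the name of the first candidate, and that term has no other use in the visible SAP. A programmer who matches the phrase to the section's own vocabulary would arrive at the decision date, which is not the protocol's anchor.

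The flag could then select different events from those the protocol defines. The adverse event tables would also cover a different period from the laboratory and vital-sign summaries and from the protocol's 30-day death table. Where the decision comes after the last dose, the added days are ones in which the protocol requires only possibly drug-related events to be reported, so what is counted there may be selectively ascertained.

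**Working it through.** There is no planned figure to reproduce. The check compares anchors and then does simple date arithmetic.

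**Anchors side by side**

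| Place | The 30 days run from |
|---|---|
| Protocol 13.3.3.1, treatment-emergent definition | last administration |
| Protocol 12.2.1, collection of all adverse events | last dose |
| SAP 3.1, safety follow-up | last administration |
| SAP 10.6.2 and 10.6.3, laboratory and vital-sign cut-offs | last administration |
| SAP Section 6, treatment-emergent definition | end of study treatment, no date named |
| SAP Section 6, closest defined term | decision to end investigational product |

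SAP Section 11 lists one departure from the protocol, the test used for ORR. It lists none for the adverse event window.

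**Length of the post-dose window**

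Let g = decision date minus last dose date.

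- Anchored on last dose: 30 days for every subject.
- Anchored on the decision date: 30 + g days.

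**Values of g (assumptions, since the documents give none)**

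Take an uninterrupted schedule and suppose the decision falls on Day 1 of the next cycle, which is Day 29 of the current 28-day cycle. On the nominal schedule this is the longest wait before another dose is due. Scheduled dosing days come from Protocol 9.2.1, Figure 3.

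- Cycles 1 to 9, both arms: the last scheduled dose is dexamethasone on Day 22. g = 29 − 22 = 7, so the window is 30 + 7 = 37 days.
- Cycle 10 on, once-weekly arm: the last scheduled dose is on Day 15. g = 29 − 15 = 14, so the window is 30 + 14 = 44 days.
- Cycle 10 on, twice-weekly arm: the last scheduled dose is on Day 16. g = 29 − 16 = 13, so the window is 30 + 13 = 43 days.
- Decision on the day of the last dose: g = 0, so the window is 30 days and nothing changes.
- Last dose 7 days after the decision: g = −7, so the window is 30 − 7 = 23 days. Protocol 9.3.2 allows dexamethasone to be tapered before it is stopped completely, so a negative g is possible.

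The ±2-day allowance on cycle starts (Protocol 9.1) moves the three positive gaps to 5–9, 12–16 and 11–15 days.

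**What falls in the difference**

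With g above zero, the extra days lie beyond last dose + 30. There Protocol 12.2.1 asks only for events judged possibly related to study drug. With g below zero, events that were routinely collected within 30 days of the last dose would lose the treatment-emergent flag.

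**The case against.** The best reply is that context settles the matter. The SAP says it details analyses outlined in the protocol, and the protocol's anchor is clear. SAP 3.1 states that "All subjects will be followed for safety for at least 30 additional days after the last study treatment administration". The laboratory and vital-sign rules use the same anchor. The treatment-emergent sentence uses an ordinary lower-case phrase without the word date, so it need not invoke the decision-date term. Only the last-dose reading avoids an undeclared change. This stands as an argument about what was probably intended. It does not remove the problem that the section's closest defined term points elsewhere, while the term that fits is defined in the same section and not named.

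A second reply also stands. SAP Appendix A, whose title covers the handling of adverse event dates, cannot be read in the supplied text. It may or may not fix the end of the window. Nothing here says that it fails to.

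Three stronger readings are tempting and are not supported:

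- A reader might infer that the SAP has deliberately changed the window. The wording permits that reading, but the context points the other way.
- A reader might infer a gap of up to 28 days from the rule on carfilzomib interruption in Protocol 9.3. That section says dexamethasone should normally continue while carfilzomib is held, and the SAP's last dose counts either drug, so a hold does not by itself create such a gap.
- A reader might infer that the extra days contain only drug-related events. Follow-up is for at least 30 days, so other events may still be recorded.

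It is also fair to say that Protocol 12.2.1 is a collection rule. An analysis window of a different length fails to match it but does not contradict it.

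**Conclusion.** The point holds for the visible wording and is minor. Read through its own closest defined term, the SAP window departs from Protocol 13.3.3.1 without a declaration in Section 11, and it does not match adverse event collection or the SAP's own laboratory and vital-sign cut-offs.

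The size is 30 + g days in place of 30. Apart from the identity at g = 0, every value of g above is an assumption, and the positive cases sit at the long end of an uninterrupted schedule. They are counts of days, not of adverse events, and the number of subjects affected cannot be derived from the documents.

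The effect is confined to the descriptive treatment-emergent tables in SAP 10.6.1 and the fatal treatment-emergent endpoint in the exposure-response work (SAP 10.7.1). The one-day difference between arms from Cycle 10 follows from the assumed decision day and is not evidence of a biased comparison. PFS, ORR and OS are untouched.

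**What to change.** In the SAP's treatment-emergent definition, replace the reference to the end of study treatment with *Last Dose Date of Study Treatment*, as Section 6 already defines it. The window then matches Protocol 13.3.3.1 and the cut-offs in SAP 10.6.2 and 10.6.3. If the decision date was intended, declare and justify that in Section 11. Check at the same time that Appendix A uses the same anchor. The cost is one phrase in the SAP and one date variable in the flag.

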7.1 Primary Analysis Set

The primary analysis of efficacy will be performed on all randomized subjects analyzed according to their randomized treatment assignment, regardless of the treatment received.

7.2 Safety Analysis Set

The primary analysis of safety will be performed on the Safety Analysis Set which will include all subjects who received at least one dose of study treatment analyzed according to the treatment they received.

7.3 Per Protocol Set

The Per Protocol Set will include all randomized subjects who did not have any important protocol deviations which could have an impact on the efficacy evaluation of the subject.

Subjects with the following protocol deviations will be excluded from the per protocol set for OS analysis:

- Inclusion criteria of relapsed multiple myeloma
- Inclusion criteria of refractory multiple myeloma
- Inclusion criteria of 2 or 3 prior therapies for multiple myeloma
- Inclusion criteria of prior exposure to an IMiD
- Inclusion criteria of prior exposure to a Proteasome Inhibitor (PI)
- Inclusion criteria of documented response of at least partial response (PR) to at least
 1 prior line of therapy.
- Inclusion criteria of measurable disease
- Exclusion criteria of second malignancy within the past 5 years
- Exclusion criteria of cytotoxic chemotherapy or other antineoplastic within 28 days prior to randomization
- Exclusion criteria of immunotherapy such as an IMiD or PI within 21 days prior to randomization

Statistical Analysis Plan: 20140355

Date: 09 Jun 2017 Page 21

 Exclusion criteria of glucocorticoid therapy exceeding a cumulative dose of 160mg within 21 days prior to randomization

- Subject received concurrent therapy with a marketed or investigational anticancer therapeutic or radiation to large marrow reserves for either a therapeutic or palliative intent while receiving study treatment
- Subject received wrong treatment other than treatment assigned to

In addition to the deviations listed above, subjects who had the following deviations will also be excluded from per-protocol set for PFS and ORR analysis:

- Subject permanently discontinued treatment due to progressive disease (PD) based on local labs not central labs
- Subject ended treatment before confirmed PD but no further disease assessments were carried out
- Baseline laboratory disease assessment was not done in such a way subject is not measurable as defined per protocol
- Subject received plasmapheresis while receiving study treatment

Subjects will be analyzed according to their randomized treatment assignment.

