Exclusion criteria:	
201. Waldenström macroglobulinemia
 
202. Multiple myeloma of Immunoglobulin M (IgM) subtype
 
203. POEMS syndrome (polyneuropathy, organomegaly, endocrinopathy, monoclonal protein, and skin changes)
 
204. Plasma cell leukemia ($> 2.0 \times 10^9/L$ circulating plasma cells by standard differential)
 
205. Myelodysplastic syndrome
 
206. Second malignancy within the past 5 years except:
 
 a. Adequately treated basal cell or squamous cell skin cancer b. Carcinoma in situ of the cervix c. Prostate cancer < Gleason score 6 with stable prostate-specific antigen (PSA) over 12 months d. Ductal breast carcinoma in situ with full surgical resection (i.e., negative margins) e. Treated medullary or papillary thyroid cancer f. Similar condition with an expectation of > 95% five-year disease-free survival 
207. History of or current amyloidosis
 
208. Cytotoxic chemotherapy or other antineoplastic therapy, aside from immunotherapy or proteasome inhibitors, within the 28 days prior to randomization
 
209. Immunotherapy, such as an IMiD or a proteasome inhibitor within the 21 days prior to randomization
 
210. Glucocorticoid therapy exceeding a cumulative dose of 160 mg of dexamethasone or equivalent within 14 days prior to randomization
 
211. Radiation therapy:
 
 a. Focal therapy within the 7 days prior to randomization b. Extended field therapy within the 21 days prior to randomization 
212. Prior treatment with either carfilzomib or oprozomib
 
213. Known history of allergy to Captisol (a cyclodextrin derivative used to solubilize carfilzomib)
 
214. Contraindication to dexamethasone or any of the required concomitant medications or supportive treatments
 
215. Active congestive heart failure (New York Heart Association [NYHA] Class III or IV, refer to Appendix F), symptomatic ischemia, conduction abnormalities uncontrolled by conventional intervention, acute diffuse infiltrative pulmonary disease, pericardial disease, or myocardial infarction within 6 months prior to randomization
 
216. Active infection requiring systemic treatment within the 14 days prior to randomization

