5.2 EXCLUSION CRITERIA

201. Waldenström macroglobulinemia
202. Multiple myeloma of Immunoglobulin M (IgM) subtype
203. POEMS syndrome (polyneuropathy, organomegaly, endocrinopathy, monoclonal protein, and skin changes)
204. Plasma cell leukemia ($> 2.0 \times 10^9/L$ circulating plasma cells by standard differential)
205. Myelodysplastic syndrome
206. Second malignancy within the past 5 years except:
 - a. Adequately treated basal cell or squamous cell skin cancer
 - b. Carcinoma in situ of the cervix
 - c. Prostate cancer $<$ Gleason score 6 with stable prostate-specific antigen (PSA) over 12 months
 - d. Ductal breast carcinoma in situ with full surgical resection (i.e., negative margins)
 - e. Treated medullary or papillary thyroid cancer
 - f. Similar condition with an expectation of $> 95\%$ five-year disease-free survival
207. History of or current amyloidosis
208. Cytotoxic chemotherapy or other antineoplastic therapy, aside from immunotherapy or proteasome inhibitors, within the 28 days prior to randomization
209. Immunotherapy, such as an IMiD, or a proteasome inhibitor, within the 21 days prior to randomization
210. Glucocorticoid therapy exceeding a cumulative dose of 160 mg dexamethasone or equivalent, within the 14 days prior to randomization
211. Radiation therapy:
 - a. Focal therapy within the 7 days prior to randomization
 - b. Extended field therapy within the 21 days prior to randomization
212. Prior treatment with either carfilzomib or oprozomib
213. Known history of allergy to Captisol (a cyclodextrin derivative used to solubilize carfilzomib)

214. Contraindication to dexamethasone or any of the required concomitant medications or supportive treatments
215. Active congestive heart failure (New York Heart Association [NYHA] Class III or IV, refer to [Appendix F](#)), symptomatic ischemia, conduction abnormalities uncontrolled by conventional intervention, acute diffuse infiltrative pulmonary disease, pericardial disease, or myocardial infarction within 6 months prior to randomization
216. Active infection requiring systemic treatment within the 14 days prior to randomization
217. Pleural effusions requiring thoracentesis within the 14 days prior to randomization
218. Ascites requiring paracentesis within the 14 days prior to randomization
219. Ongoing graft-versus-host disease
220. Uncontrolled hypertension or diabetes mellitus
221. Significant neuropathy (\geq Grade 3) within the 14 days prior to randomization
222. Known cirrhosis

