10.3 Important Protocol Deviations

Important Protocol Deviations (IPDs) categories are defined by the study team before the first subject's visit and updated during the IPD reviews throughout the study prior to database lock. These definitions of IPD categories, sub-category codes, and descriptions will be used during the course of the study. Eligibility deviations are defined in the protocol.

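### SAP 7.3 gives the glucocorticoid exclusion a 21-day window, protocol criterion 210 gives 14 days; applied literally, the SAP bullet could drop eligible subjects from the per-protocol sensitivity analyses of PFS, ORR and OS

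*SAP*

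**What the plan says.** Protocol Section 5.2, criterion 210, excludes "Glucocorticoid therapy exceeding a cumulative dose of 160 mg dexamethasone or equivalent, within the 14 days prior to randomization". The synopsis agrees: "Glucocorticoid therapy exceeding a cumulative dose of 160 mg of dexamethasone or equivalent within 14 days prior to randomization".

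SAP Section 7.3 defines the per-protocol set as randomized subjects free of important protocol deviations that could affect the efficacy evaluation. It then lists the deviations under the lead-in "Subjects with the following protocol deviations will be excluded from the per protocol set for OS analysis". One of them is "Exclusion criteria of glucocorticoid therapy exceeding a cumulative dose of 160mg within 21 days prior to randomization".

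The list is extended to the other two tested endpoints: "In addition to the deviations listed above, subjects who had the following deviations will also be excluded from per-protocol set for PFS and ORR analysis". SAP Table 5 names the per-protocol analysis as a sensitivity analysis for PFS, ORR and OS.

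On where eligibility deviations come from, SAP Section 10.3 says: "Eligibility deviations are defined in the protocol".

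**The concern.** The SAP bullet presents itself as a breach of a protocol exclusion criterion but states a different window from that criterion. A per-protocol set is meant to remove people who departed from the protocol. A rule wider than the protocol can also remove people who complied with it.

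At stake is whether the three per-protocol sensitivity analyses have a single, reproducible population. As the SAP stands, a programmer who codes the Section 7.3 bullet gets one set, and a programmer who uses the protocol's definition, as Section 10.3 directs, may get another. In an open-label trial, membership of an analysis set should be settled before analysis and should not depend on which section is read.

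**Working it through.** The documents give no figure to reproduce here, so the check is a comparison of the texts followed by a logic test.

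**Washout windows side by side**

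| Criterion | Protocol 5.2 | SAP 7.3 | Agree? |
|---|---|---|---|
| 208, chemotherapy or other antineoplastic | 28 days | 28 days | yes |
| 209, immunotherapy, IMiD or PI | 21 days | 21 days | yes |
| 210, glucocorticoid above 160 mg cumulative | 14 days | 21 days | **no** |

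For criterion 209 the protocol has "Immunotherapy, such as an IMiD, or a proteasome inhibitor, within the 21 days prior to randomization" and the SAP has "Exclusion criteria of immunotherapy such as an IMiD or PI within 21 days prior to randomization". Only the steroid bullet departs from the protocol, and its 21 days equals the window in the bullet directly above it. A carry-over slip is plausible, but the documents do not say so.

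**Is there a source for 21 days?** None was found. SAP Section 11, which records changes from the protocol-specified analyses, names only the ORR test. The change log in Protocol Appendix O shows that the superseded wording of criterion 210 also used 14 days.

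**Which way the mismatch runs.** Let D14 and D21 be a subject's cumulative dose over the 14 and 21 days before randomization.

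- D21 = D14 + dose on days -21 to -15, so D21 ≥ D14.
- Protocol rule: flagged if D14 > 160 mg.
- SAP rule as written: flagged if D21 > 160 mg.
- Everyone flagged by the protocol rule is therefore flagged by the SAP rule. The subjects on whom the rules differ are those with D14 ≤ 160 mg < D21.

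**Illustration.** These dosing histories are assumptions, not trial data; doses are in mg of dexamethasone.

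| History | D14 | D21 | Protocol 210 | SAP 7.3 as written |
|---|---|---|---|---|
| A: 40 on days -21 to -18, 40 on day -10 | 40 | 4 × 40 + 40 = 200 | eligible | removed |
| B: 40 on days -21, -14 and -7 | 2 × 40 = 80 | 3 × 40 = 120 | eligible | kept |
| C: 40 on days -18 to -15, 40 on day -4 | 40 | 4 × 40 + 40 = 200 | eligible | removed |
| D: 40 on days -10 to -6 | 5 × 40 = 200 | 200 | excluded | removed |

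A and C are the affected pattern. B shows that exposure in days -21 to -15 is not enough by itself: the 21-day total must pass 160 mg. Four doses of 40 mg alone give exactly 160 mg, which does not exceed the threshold under either rule.

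**After the fix.** With one window in both documents the two rules flag the same subjects, and the D14 ≤ 160 mg < D21 group is no longer removed on this ground.

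**The case against.** The strongest reply is that the bullet does not stand alone. It sits under a lead-in about protocol deviations, the set is defined by important protocol deviations, and SAP Section 10.3 sends the reader to the protocol for eligibility deviations. On that reading a subject who met criterion 210 has no deviation and stays in the set, whatever the bullet says. This stands in part: removal is possible, not certain, and depends on the bullet being coded literally. It does not clear the text, because it leaves Sections 7.3 and 10.3 pointing to different rules.

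A reader might also infer that, because the bullet omits the dexamethasone-equivalent basis, 160 mg of a weaker steroid would remove a subject. The documents do not support that. The eligibility bullets in Section 7.3 are short labels: the second-malignancy bullet drops all six exceptions in criterion 206, and the chemotherapy bullet drops the carve-out in criterion 208. The omission is shorthand, worth tidying when the window is corrected.

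Finally, the per-protocol analysis is one of seven sensitivity analyses listed for PFS in Table 5, one of four for ORR and one of two for OS. That is correct and limits the weight of the point.

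**Conclusion.** The contradiction between 21 and 14 days is exact and undeclared. Applied as written, SAP 7.3 could remove subjects who satisfied criterion 210 from the per-protocol sets for OS, PFS and ORR. The conclusion rests on one condition, that the bullet is coded literally, and concerns only subjects above 160 mg over 21 days but not over 14.

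The size is unknown. A reader might apply a guessed rate to the 460 planned subjects; 1% to 5% would give 0.01 × 460 = 4.6 to 0.05 × 460 = 23. Nothing in the documents supports such a rate. They hold no pre-randomization steroid data, and the count may be zero.

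Nor should a reader infer any threat to the main result. SAP Section 7.1 bases the primary efficacy analysis on all randomized subjects, so the tests, the power and the type I error control do not depend on this bullet. This is a wrong analysis-set rule confined to sensitivity analyses. Which washout window is clinically appropriate is not judged here.

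**What to change.** Before database lock, reconcile the SAP 7.3 glucocorticoid bullet with protocol criterion 210. Because SAP Section 10.3 makes the protocol the source for eligibility deviations, the bullet should cite criterion 210 by number and carry its wording, for both the window and the dexamethasone-equivalent basis. The per-protocol set then removes, on this ground, only subjects who violated the protocol's own criterion.

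The cost is one line in the SAP and a check that the deviation flag is programmed to match. No other analysis changes.
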